8.3.2 Efficacy Analysis

8.3.2.1 Primary Efficacy Analysis

The primary hypothesis for this study is that JBT-101 treatment will result in improvement in the maximum daily pain NRS scores in SLE patients with active musculoskeletal disease. The null hypothesis to be tested is:

H0: Linear trends from Day 1 to Day 84 are equivalent for each JBT-101 cohort and placebo. HA: Linear trends from Day 1 to Day 84 are not equivalent across groups.

In addition, pairwise comparisons of each JBT-101 cohort versus placebo are of key interest.

For the primary analysis, the maximum daily pain NRS scores from Day 1 through end of treatment (typically Day 84) will be modeled using a random regression approach. The fixed

effects model will include treatment group, time, time², time- and time² by treatment group interactions, as well as the Screening 7-day average maximum daily pain NRS as a covariate. Within-subject random effects for intercept and slopes for time and time² will be fit using an unstructured covariance matrix assuming the same structure for all treatment groups. In the event of convergence problems, the covariance structure will be simplified by dropping the random effect for time². The primary hypothesis will be tested using the 3 degrees of freedom contrast comparing the difference in predicted means ($\hat{\mu}$) from Day 1 to Day 84 for each JBT-101 group versus placebo. That is, ($\hat{\mu}_{84} - \hat{\mu}_1$)_{cohort i}- ($\hat{\mu}_{84} - \hat{\mu}_1$)_{placebo} = 0 for i=1 to 3.

NRS data up to the day of last dose of study treatment will be included in the analysis for all subjects in the mITT population. Any NRS data entered into the IVRS after discontinuation of study treatment or entered on days when narcotic analgesics were taken will be excluded. If the 3 df test is significant, Dunnett's tests for 1 df pairwise comparisons with placebo are planned. If the 3 df test is not statistically significant, confidence intervals for the 1df pairwise comparisons with placebo will still be presented, but this information will be used for hypothesis generation and planning of future studies.

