from this study is impractical and would delay and jeopardize completion of study enrollment. Multiple steps have been included in the trial design to account for the potential impact of pain from fibromyalgia on study results. To ensure that a significant component of the subjects daily pain NRS score is from inflammatory pain from joint/tendon involvements, subjects will be required to have arthritis and/or tendonitis on SELENA SLEDAI assessment or B score in the musculoskeletal domain of the BILAG 2004 assessment. The presence or absence of fibromyalgia and its severity will be assessed using the Fibromyalgia Symptom Score [107]. The absence versus presence of fibromyalgia (Fibromyalgia Symptom Score < 13 versus \geq 13 at Screening) will be used as a stratification variable at randomization and in subset analyses of the efficacy outcomes.

1.6.2 **Rationale for the Treatment Arm**

The JBT-101 doses selected for this study are within the range of doses that were well tolerated in previous Phase 1 and 2 studies and in a recently completed clinical trial in SSc, all sponsored by Corbus Pharmaceuticals Holdings, Inc. The JBT-101 oral doses selected for this study are 5 mg b.i.d., 20 mg q.d., and 20 mg b.i.d. Parallel dose assignment to JBT-101 in doses up to 20 mg b.i.d. is supported by a previous multiple ascending dose study and a Phase 2 study in humans in which JBT-101 doses up to 40 mg b.i.d. showed acceptable safety profiles and were well-tolerated. In a recently completed study of JBT-101 in systemic sclerosis and ongoing studies in dermatomyositis and cystic fibrosis (sponsored by Corbus) using similar doses to those proposed in this clinical trial (5 mg-40 mg daily), JBT-101 has been well tolerated with no severe AEs attributable to JBT-101. Each dose is expected have an acceptable safety profile, be well-tolerated, and provide clinical benefit, based on previous animal or human testing and the nature of the inflammatory components of SLE. Based on preclinical data and early higher dose clinical data, it is expected that any safety risk and clinical efficacy of JBT-101 in humans will be related to exposure. Based on extrapolation from animal models of inflammation, 5 mg q.d. was estimated to be about the median dose required for efficacy in humans. However, information from the cystic fibrosis study and from a cutaneous model of E. coli- induced inflammation [101] suggests that 5 mg b.i.d. may be more effective than the 5 mg q.d. dose:

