3.1.1 Stratification, Randomization, and Blinding

Eligible subjects will be randomized in a 1:1:1:1 ratio to one of four cohorts: 5 mg JBT-101 b.i.d., 20 mg JBT-101 q.d., 20 mg JBT-101 b.i.d., or placebo (see Section 3.1, *Description of Study Design*, Table 1). Subjects will be stratified by 7-day average of maximum daily pain NRS score ≤ 6 versus > 6 and Fibromyalgia Symptom Scale Score < 13 versus ≥ 13 at Screening.

To maintain the study blind, JBT-101 and placebo capsules and their packaging will be identical. All subjects will receive b.i.d dosing to maintain blinding to treatment assignment. In general, clinical staff, including the investigators, will be blinded to the treatment assignments until completion of the study. In addition, they will not have access to any mechanistic data, and mechanistic laboratory staff will not have access to any clinical results until completion of the study. The success of blinding will be formally tested using a Treatment Satisfaction Survey that asks each study subject and corresponding site investigator to guess the study group assignment for that subject at the end of active treatment and then comparing these responses to what would be expected by chance.

Unblinding must be approved by the study Medical Monitor unless an immediate life threatening condition has developed and the Medical Monitor is not accessible. The site investigator will notify the protocol chair(s) and the DAIT- Statistical and Clinical Coordinating Center (SACCC) of the unblinding event on the next business day. The emergency unblinding will also be reported to the Data and Safety Monitoring Board (DSMB).

A full account of the event will be recorded, including the date and time of the unblinding, the reason for the decision to unblind, and the name of the individual who made the decision and the names of the Medical Monitor and others who were notified. The reasons for unblinding of a participant's treatment will be included in the final study report.

An individual's treatment assignment will be unblinded if the subject experiences a suspected adverse reaction that is serious and unexpected (see Section 7.2.1, *Adverse Event* and Section 7.2.1.1 *Suspected Adverse Reaction* and Section 7.2.2, *Unexpected Adverse Event*) or other protocol-specific event(s) determined by DAIT/NIAID to warrant unblinding.

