JBT-101 group 3	-d	-d						

Table 6: Treatment Effect Scenarios

[figure not shown]
Using the covariance parameters for pooled, best and worst cases (Table 5) and treatment effects for Scenarios 1 and 2 (Table 6), we generated non-centrality parameters for the F statistic for evaluating the 3 df test, and computed power according to the method of Stroup (1999). Power estimates for a Type 1 error rate = 0.05 and treatment group sizes of 22 and 25 are displayed in Figure 3. The x axis ranges from 1.5 to 2.0 (i.e. values of d) and represents the maximum difference between treatment versus placebo for 1 JBT-101 treated group in Scenario 1 or 2 treated groups in Scenario 2. The y axis displays associated power.

When 2 JBT-101 treated groups achieve the target treatment effect (Scenario 2), power exceeds 80% for treatment effects of at least 1.6 using the pooled SD with 25 per group (Figure 3a). These estimates assume complete data for each subject. Given that this study is of relatively short duration, subject retention is expected to be good with minimal data missing. However, if the sample size drops to 22 per group due to missing data or withdrawals, minimum power is still nearly 80%. If only 1 JBT-101 treated group achieves the target treatment effect (Scenario 1), then a treatment effect of at least 1.9 would be needed for 80% power on the 3 df test.

[figure not shown]
This analysis does not take into account that the random regression model will include the Screening 7-day average maximum daily pain NRS as a covariate as well as terms for quadratic trends in time, both of which will account for a fraction of the variance in the NRS scores and, hence, may reduce the residual variance and increase power. Figure 3b shows the impact of a small reduction in residual variance from 0.49 to 0.41 (Table 5). For Scenario 2, power exceeds 80% for treatment effects of at least 1.5 with 22 or 25 per group. If only 1 JBT-101 treated group achieves the target treatment effect (Scenario 1), then a treatment effect of at least 1.7 gives power of ~80% or better.

[figure not shown]

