8.3 Description of the Analyses

- All data will be provided in data listings sorted by treatment groups, subject number, and visit.
- Summary data will be presented in tabular format by treatment groups.

- Categorical data will be summarized by the number and percentage of subjects in each category.
- Continuous data will be summarized by descriptive statistics including N, mean, standard deviation, median, and range.
- All percentages will be rounded to one decimal place.
- Differences between groups will be calculated as active placebo and change from baseline (ΔNRS) will be calculated as follow-up visit – baseline.
- The baseline measure will be defined as the last non-missing measure prior to initiation of study product. It is expected that baseline values for efficacy assessments will be measured at Visit 1 (Day 1).
- P-values will be assessed at a 2-sided alpha = 0.05 level for the primary efficacy analysis.
- Secondary analyses are exploratory and intended to deepen our understanding of risks and benefits, to refine hypotheses, and to obtain information from which to design, select doses, and power future pivotal studies. P-values will be presented for secondary efficacy analyses. No adjustments for multiple comparisons are planned for secondary analyses.

8.3.1 **Subject Disposition**

The disposition of all subjects over the course of the trial will be summarized by cohort and overall. The number and percent of subjects in each analysis population (mITT, PP, safety, and PK) will be displayed. In addition, the presentation will include the number of subjects who completed the study, the number who withdrew prematurely from the study, as well as the reason for withdrawal. In addition, the number of subjects who continued treatment to Visit 5 (Day 85) and who discontinued treatment early will also be summarized along with reasons for discontinuation.

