8.5 Other Statistical Considerations

8.6 Covariates

No specific adjustments for covariates are planned for this study.

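### Fibromyalgia status stratifies the randomization but is absent from the primary pain model, which makes the 3 df test mildly conservative if that status predicts pain change; Section 8.6 also contradicts the model it covers

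*Protocol*

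**What the plan says.** Section 3.1.1 sets two stratification factors: "Subjects will be stratified by 7-day average of maximum daily pain NRS score ≤ 6 versus > 6 and Fibromyalgia Symptom Scale Score", the latter cut as "Fibromyalgia Symptom Scale Score < 13 versus ≥ 13 at Screening". Section 1.6.1 gives the reason. Subjects with fibromyalgia are admitted, and the design takes several steps to allow for the effect their pain may have on the results. Fibromyalgia status "will be used as a stratification variable at randomization and in subset analyses of the efficacy outcomes".

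Section 8.3.2.1 lists the fixed effects of the primary random regression in full: the "effects model will include treatment group, time, time², time- and time² by treatment group interactions, as well as the Screening 7-day average" of maximum daily pain. Fibromyalgia is not in the list. The test is defined there as follows: "The primary hypothesis will be tested using the 3 degrees of freedom contrast comparing the difference in predicted means" from Day 1 to Day 84, each JBT-101 group against placebo. Elsewhere in Section 8, fibromyalgia appears only as a possible covariate for secondary endpoints (8.3.2.2) and as a subgroup (8.9).

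Section 8.6 reads in full: "No specific adjustments for covariates are planned for this study".

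**The concern.** Stratified randomization balances the arms on fibromyalgia status. If that status also predicts how pain changes over the 84 days, balance removes the between-stratum variation from the true sampling error of the arm contrasts. A model without the factor still counts that variation as error. Its standard errors are then wider than they need be, and the nominal 5% test rejects less than 5% of the time under the null hypothesis.

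Precision matters here because Section 8.1 places the primary test only just above 80% power in its reference case (Scenario 2, effect 1.6, pooled SD, 25 per group). The variable is already collected at Screening for every subject.

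Section 8.6 is a separate, purely textual matter. It rules out covariate adjustment, while Section 8.3.2.1 adjusts for Screening pain.

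**Working it through.** **Inputs from the protocol.** Table 5, pooled row: slope variance 0.00063 and residual variance 0.49. Table 6, Scenario 2 with d = 1.6: arm means 0, −0.4, −1.6, −1.6. Group size 25 ("Power estimates for a Type 1 error rate = 0.05 and treatment group sizes of 22 and 25 are displayed in Figure 3"). Alpha: "P-values will be assessed at a 2-sided alpha = 0.05 level for the primary efficacy analysis". Complete data, as Section 8.1 assumes. Fibromyalgia prevalence 16–32% of SLE patients (Section 1.1.1).

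**Assumptions not in the protocol.** The enrolled prevalence lies in that 16–32% range. D, the difference between fibromyalgia strata in mean 84-day pain change, is 0, 0.5, 1 or 2 NRS points. Strata are equally represented in each arm. The calculation uses linear time, as the power section does.

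**Step 1: reproduce the stated power.**
- Sum of squares of days 1 to 84: 84 × (84² − 1)/12 = 49,385.
- Variance of a subject's change over L days: v = L² × (0.00063 + 0.49/49,385). L = 84 gives 4.515 (SD 2.125); L = 83 gives 4.408 (SD 2.100).
- The mean of the arm means is −0.9, so the sum of squared deviations is 0.81 + 0.25 + 0.49 + 0.49 = 2.04.
- Noncentrality: 25 × 2.04/v = 11.29 (L = 84) or 11.57 (L = 83).
- Power from the noncentral F with 3 and 96 df: 0.798 or 0.808. The protocol says power exceeds 80%, so its figure reproduces.
- Standard error of one dose-versus-placebo contrast: √(2v/25) = 0.601 (L = 84) or 0.594 (L = 83).

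**Step 2: fibromyalgia as a main effect only.** A constant difference in pain level cancels from a Day 84 minus Day 1 contrast. Generalized least squares on 84 daily measures for 100 subjects confirms this. With L = 83 the standard error is 0.594 without and 0.594 with the term. With 12% dropout it is 0.597 and 0.597, even if fibromyalgia explains 0.5 of the 2.35 intercept variance. The gain is nil.

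**Step 3: fibromyalgia with its time interaction.** Holding total variance at Table 5, the share of the variance of change explained by the stratum is R² = p(1 − p)D²/v, with v = 4.515. For p = 0.32 and D = 1, R² = 0.2176/4.515 = 0.048. The adjusted standard error is 0.601 × √(1 − R²). Power uses v(1 − R²) with 3 and 95 df.

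| Prevalence | D (NRS points) | R² | Adjusted SE | Power after adjustment |
|---|---|---|---|---|
| either | 0 | 0 | 0.601 | 0.797 |
| 32% | 0.5 | 0.012 | 0.597 | 0.803 |
| 32% | 1 | 0.048 | 0.586 | 0.819 |
| 32% | 2 | 0.193 | 0.540 | 0.882 |
| 16% | 1 | 0.030 | 0.592 | 0.811 |
| 16% | 2 | 0.119 | 0.564 | 0.850 |

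Unadjusted power on the same basis is 0.798.

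**Step 4: actual level when the factor is omitted.** In 40,000 simulated trials with equal fibromyalgia counts per arm, the nominal 5% test rejected in 0.050, 0.048, 0.042 and 0.021 of runs for D = 0, 0.5, 1 and 2. Model standard error against true standard deviation was 0.600 against 0.599 (D = 0.5), 0.600 against 0.587 (D = 1) and 0.602 against 0.536 (D = 2). The formula P(F(3,96) > 2.699/(1 − R²)) at 32% prevalence agrees: 0.048, 0.042 and 0.022.

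**The case against.** The strongest objection is that the premise is not in the protocol. Section 1.6.1 speaks of fibromyalgia pain possibly affecting results, which is about the level and source of pain. Nothing says that fibromyalgia predicts change, and change is what the primary contrast tests. This stands, and it is why the point is conditional.

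A reader might go further and infer that the primary intervals are certainly too wide, or that adjustment would buy five or ten points of power. The documents do not support either. A correlation ρ between stratum and slope converts to a stratum difference D = ρ × 83 × √0.00063/√(p(1 − p)), where 83 × √0.00063 = 2.08. A five-point gain needs ρ of about 0.35, so D is about 1.6 (32% prevalence) to 2.0 (16%), which is as large as the drug effect of 1.6 in the reference case. A ρ of 0.5 would give about 91% power but needs D of 2.2 to 2.8, above the 2-point individual improvement that Section 8.1 treats as clinically important.

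It can also be said that any error is conservative, that Section 8.1 openly accepts limited power for a first Phase 2 study in SLE, and that fibromyalgia is examined in subgroups and may enter secondary models. All true. They limit the seriousness of the omission but give no reason for it.

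Last, Section 8.1 expects the Screening pain covariate and quadratic terms to lower residual variance and perhaps raise power. Cutting the residual alone from 0.49 to 0.41 moves power only from 0.798 to 0.799, because slope variance dominates. Terms that explain slopes are the ones that can help.

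On Section 8.6, the explicit model in 8.3.2.1 tells the analyst what to fit, so the harm is small; the two statements still cannot both be right.

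**Conclusion.** The point holds in conditional form. A stratification factor is missing from a primary model that the protocol spells out term by term, and Section 8.6 is inconsistent with that model. For stratum differences up to 1 NRS point the loss is small: a standard error 1.5% (16% prevalence) to 2.4% (32%) wider than necessary, one to two points of power, and, at 32% prevalence, a true level no lower than about 0.042. It becomes material only near a 2-point difference, with power of 85–88% after adjustment against about 80% without. The estimates are not biased and type I error is not inflated. These sizes rest on the assumed D and enrolled prevalence, equal stratum counts per arm, complete data and linear time. The change is worth making because it is nearly free, not because a large loss has been shown.

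**What to change.** In Section 8.3.2.1, add the Screening fibromyalgia stratum (<13 versus ≥13) to the fixed effects together with its interactions with time and time². The interactions are essential, since a main effect alone does nothing for the tested contrast. Use the Screening classification applied at randomization; Section 8.9 dates its fibromyalgia split at Visit 1. In Section 8.6, replace the statement that no adjustment is planned with the list of covariates in the primary model.

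The cost is wording and about three fixed-effect parameters, with no new data. If fibromyalgia turns out not to predict pain change, essentially nothing is lost (power 0.798 before, 0.797 after). The change should be fixed before unblinding.

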Study Design: One hundred eligible subjects will be randomized in a 1:1:1:1 ratio to one of four cohorts to receive either JBT-101 (three groups: 5 mg q a.m. and 5 mg q p.m., 20 mg q a.m. and placebo q p.m., 20 mg q a.m. and 20 mg q p.m.) or placebo for 84 days, then 28 days of follow-up. Subject visits to assess endpoints occur at six times: Days 1, 15 ± 3 , 29 ± 3 , 57 ± 3 , 85 ± 3 and 113 ± 3 .

Endpoints:

PRIMARY EFFICACY ENDPOINT:

The primary endpoint for evaluation of the primary objective will be improvement in maximum daily pain NRS scores in the treated groups relative to the control after 12 weeks of treatment. Longitudinal trends over the course of the treatment period will be modeled and used to estimate differences between means at baseline and Day 84 for each treatment group.

SECONDARY EFFICACY ENDPOINTS:

- 1. The 7-day average of maximum daily pain NRS scores prior to Visits 1 (Day 1), 3 (Day 29), 4 (Day 57), 5 (Day 85), and 6 (Day 113) will be used to evaluate the number (%) of subjects with:
 - Changes in pain categories from Visit 1 (Day 1) to Visits 3 (Day 29), 4 (Day 57), 5 (Day 85) and 6 (Day 113) (See Section 6.2.2.2 *Pain Categories*)
 - Improvement of 30% from Visit 1 (Day 1) to Visits 3 (Day 29), 4 (Day 57), 5 (Day 85) and 6 (Day 113)
 - Improvement of 50% from Visit 1 (Day 1) to Visits 3 (Day 29), 4 (Day 57), 5 (Day 85) and 6 (Day 113)
 - Improvement of 75% from Visit 1 (Day 1) to Visits 3 (Day 29), 4 (Day 57), 5 (Day 85) and 6 (Day 113)
 - Improvement of 100% from Visit 1 (Day 1) to Visits 3 (Day 29), 4 (Day 57), 5 (Day 85) and 6 (Day 113)
- 2. Trends in active musculoskeletal disease activity over the duration of the treatment period (i.e. Visit 1 (Day 1) through Visit 5 (Day 85)) will be evaluated longitudinally using multiple indices:
 - Physician assessed tender joint count
 - Physician assessed swollen joint count
 - Presence or absence of arthritis on the SELENA SLEDAI
 - Musculoskeletal domain of the BILAG 2004
- 3. Persistence of trends in musculoskeletal disease activity after stopping treatment will be evaluated at Visit 6 (Day 113)
- 4. Trends in overall SLE disease activity over the duration of the treatment period (i.e. Visit 1 (Day 1) through Visit 5 (Day 85)) will be evaluated longitudinally using multiple indices:
 - SLE Responder Index , where a responder is defined as having all of the following:
 ≥4 point reduction in SELENA-SLEDAI score,
 - o no new BILAG A or no more than 1 new BILAG B domain score, and

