3.2 Description of Endpoints

See Section 6, *Assessment of Safety and Efficacy*, for detailed descriptions of endpoint measures, and Section 8, *Statistical Considerations and Analytical Plan*, for planned analyses.

3.2.1 **Primary Efficacy Endpoint**

The primary endpoint for evaluation of the primary objective will be improvement in maximum daily pain NRS scores in the treated groups relative to the control after 12 weeks of treatment. Longitudinal trends over the course of the treatment period will be modeled and used to estimate differences between means at baseline and Day 84 for each treatment group.

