5.3 Administration of Study Product

JBT-101 will be self-administered orally b.i.d., with at least 8 hours between doses and without regard to fed state. See Section 3.1, *Description of Study Design*; Table 1 for morning and evening dosing for the 4 cohorts. The first dose of JBT-101 at Visit 1 (Day 1) will be taken in the clinic, and the subjects will be observed in the clinic for at least 30 minutes after this dose or longer, until, in the opinion of the investigator, vital signs and clinical symptoms are acceptable for the subject to leave the clinic. After this observation period, subjects must still be available for additional assessments 2.5 to 3.5 hours after administration of the study product.

JBT-101 should be taken in the following way:

- JBT-101 and placebo capsules should be swallowed whole, with liquid as helpful, and should not be broken, chewed or opened. Morning and evening doses should be at least 8 hours apart.
- If a dose of JBT-101 or placebo is missed, it should be taken as soon as possible on the same day, as long as the other dose that day can be timed to be at least 8 hours separate from the time of the missed dose. If it is missed for the entire day, it should not be made up.
- Doses can be taken without regard to fed state.

Subjects who take more than the prescribed dose of JBT-101 or placebo should be instructed to seek emergency medical care, if needed, and to contact the study staff as soon as possible.

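### The primary contrast starts from a Day 1 mean fitted to scores from Day 1 on, not from the pre-dose baseline, so the share of 12-week benefit it reads depends on onset shape and is smallest for benefit building gradually from the first dose

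*Protocol*

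**What the plan says.** Section 8.3.2.1 fixes the data, the model, the null hypothesis and the contrast:

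- **Data:** "the maximum daily pain NRS scores from Day 1 through end of treatment (typically Day 84) will be modeled using a random regression approach". No pre-dose score is an outcome.
- **Model:** treatment group, time, time squared and their interactions with treatment. The Screening 7-day average is an additive covariate.
- **Null hypothesis:** "Linear trends from Day 1 to Day 84 are equivalent for each JBT-101 cohort and placebo".
- **Contrast:** "The primary hypothesis will be tested using the 3 degrees of freedom contrast comparing the difference in predicted means", that is, fitted Day 84 minus fitted Day 1 in each JBT-101 group, less the same quantity in placebo.

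Section 8.3 says: "The baseline measure will be defined as the last non-missing measure prior to initiation of study product". It expects that value at Visit 1. The Synopsis gives the primary endpoint as "improvement in maximum daily pain NRS scores in the treated groups relative to the control after 12 weeks of treatment", and section 3.2.1 adds that modelled trends will be "used to estimate differences between means at baseline and Day 84 for each treatment group".

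On timing, section 5.3 says: "The first dose of JBT-101 at Visit 1 (Day 1) will be taken in the clinic". Sections 3.1 and 6.2.1 have the diary entered in the evening, preferably at bedtime, with about 24 hours' recall. The Day 1 entry therefore normally follows the first dose, though its recall also covers some pre-dose hours.

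Section 3.2.2 already defines a 7-day average before Visit 1, but only for secondary endpoints.

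**The concern.** The endpoint text and the baseline definition point to a pre-dose reference. The tested quantity uses a fitted Day 1 value that borrows from roughly the first two weeks of treatment. With a free treatment intercept, an early gap between arms goes into that value and is then subtracted. The Screening covariate does not restore the anchor: it has no time interaction, so with complete data it cancels in the Day 84 minus Day 1 difference.

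A drug that eases pain early and holds the gain to Day 84 meets the stated endpoint but may fail the primary test. Section 1.6 says that this first study in SLE will inform whether development continues, so a false negative would be costly.

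**Working it through.** **Inputs.** Section 8.1: 25 per arm, alpha 0.05, SD 1.43, AR(1) with r = 0.9775, d from 1.5 to 2.0 points over 84 days. Scenario 2 effects are 0, 0.25d, d, d. Onset shapes are my assumptions.

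**1. The plan's own figure.** Power comes from the noncentral F with 3 numerator df and λ = n·Σ(eᵢ − ē)²/v, where v is the per-subject variance of the contrast. Scenario 2 gives Σ = 0.797d². With the pooled Table 5 covariance, d = 1.6 and a straight line, power is 81.5% (residual df) or 79.8% (96 df). The protocol says it exceeds 80%, so its figure is reproduced.

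**2. What fitted Day 1 contains.** Least-squares weights for {1, t, t²} on Days 1–84 equal the mixed-model fixed effects for complete balanced data. In fitted Day 1 the Day 1 score has weight 0.102, Days 1–14 together 1.025, and later days net −0.025. The end-minus-start weights from the quadratic and from a straight line agree to 2×10⁻¹⁶, so only the linear component is tested. For a 14-day ramp, fitted Day 1 already holds 46% of the effect and fitted Day 84 holds 86%. The contrast keeps 86.4 − 45.5 = 41% after rounding.

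**3. Share of the sustained Day 84 effect kept by the planned contrast.**

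| Assumed onset | Kept |
|---|---|
| Even ramp from first dose, complete Day 7/14/21/28/35/42 | 20/41/59/75/87/97% |
| Exponential, 90% reached by Day 21/28 | 48/59% |
| Ramp over Days 3–28, 7–28, 10–28, 14–28 | 83/93/100/108% |
| Step at Day 7/14/19/21/28 | 39/78/100/108/129% |
| Full effect in the Day 1 score | 0% |

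With 12% dropout spread over treatment and 15% of days missing at random (the 15% is an assumption), even ramps of 14/21/28 days keep 38/57/73%.

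**4. Power, Scenario 2, d = 1.6, 25 per arm, AR(1), 96 df.** Planned contrast: v = 4.44, so λ = 25 × 0.797 × 2.56 × k²/4.44 = 11.5k², with k the kept share. Predicted Day 84 difference adjusted for the 7-day pre-dose mean: v = 2.45, so λ = 20.8m², with m the share in fitted Day 84.

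| Onset | k | Planned | m | Day 84, adjusted |
|---|---|---|---|---|
| Ramp to Day 14 | 0.410 | 18% | 0.864 | 92% |
| Ramp to Day 21 | 0.591 | 35% | 0.848 | 90% |
| Ramp to Day 28 | 0.745 | 53% | 0.861 | 91% |
| Steady, t/84 | 0.988 | 79% | 1.00 | 97% |

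In 4,000 simulated trials the planned/proposed figures were 17/91%, 36/90%, 53/92% and 79/97%, with type I error 5.0/4.8%. At d = 2.0 the planned contrast has 27/52/74% for the three ramps.

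**5. Separating reference point from variance.** Holding v at 4.44 for the Day 84 contrast gives λ = 11.5m², and power for the three ramps is about 65–67%. The reference point alone therefore lifts 18%, 35% and 53% to about two thirds; the remainder is variance reduction.

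**6. Sensitivity to correlation.** AR(1) implies a Day 1–Day 84 correlation of 0.9775⁸³ = 0.15. At 0.30/0.50/0.60, planned power at d = 1.6 is 21/29/35% (14-day ramp), 41/56/66% (21-day) and 62/78/87% (28-day). The variance saving falls from (4.44 − 2.45)/4.44 = 45% to (2.09 − 1.50)/2.09 = 28% at 0.60.

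**The case against.** The null hypothesis is about linear trends, section 2.1 speaks of longitudinal changes, section 3.2.1 asks for modelled trends, section 6.2.2.2 equates baseline with Visit 1, and the power calculation uses the same slope. On that reading the contrast is deliberate and internally coherent. This stands in part: hypothesis, contrast and power basis agree with each other, and the mismatch lies only in the reference point.

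A reader might infer that any benefit complete by Day 28 is under-read by a quarter or more. The protocol does not support that. The loss belongs to onset at or near the first dose. A lag of three days raises the kept share of a 28-day build-up from 75% to 83%, a one-week lag to 93%, and later or abrupt onset is over-read. Nor does section 1.6 supply the harmful shape: its expectations of change within days or a few weeks concern biomarkers, and pain could follow with a lag.

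A reader might also infer that the stated power is wrong. It is right for the straight-line accrual it assumes.

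The responder and pain-category analyses in section 8.3.2.2 use the pre-Visit 1 average and could show an early sustained benefit. They are exploratory and do not carry the primary p-value. The percent-change analysis is built like the primary one and would inherit the subtraction.

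**Conclusion.** The point holds in conditional form. The contrast does not reliably measure the 12-week benefit named in the endpoint: depending on onset, it reads from 0% to 129% of the same sustained Day 84 effect in the shapes checked. The serious loss of power is for benefit that starts at or near the first dose, builds gradually and is complete within about two to three weeks: about 18–35% at d = 1.6 against about 79% for steady accrual.

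This rests on assumed onset shapes and on the protocol's AR(1) structure. The two-week loss persists if scores are more persistent than assumed; the loss at three to four weeks shrinks. Type I error is not affected. Worth fixing; confidence is moderate, because the protocol gives no time course for pain.

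**What to change.** Keep the random regression and the 3 df test. Make the primary contrast the predicted Day 84 difference of each JBT-101 group against placebo, and add to the model the 7-day average NRS before first dose with its interactions with time and time squared. Name that average as baseline in the Synopsis and section 3.2.1, reword the null hypothesis and contrast in section 8.3.2.1, restate the power basis in section 8.1, and carry the change into the SAP. Report the Day 1-to-84 contrast as supportive.

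No new patients or data are needed: diary scores run from Screening, and the pre-Visit 1 average is already required for secondary endpoints. The costs are these:

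- The primary estimand wording changes and must be settled before database lock.
- Comparability at the start rests on randomisation plus the covariate.
- The quadratic still under-reads fast-onset Day 84 effects by about 8–20%. For some lagged onsets it reads less than the planned contrast (84% against 93% for Days 7–28; 86% against 108% for Days 14–28).
- Part of the power gain is variance reduction that depends on AR(1), including all of the gain under steady accrual apart from the 1.2% in k.

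Across the shapes checked, power at d = 1.6 under AR(1) is 86–97% for this contrast, against 5–96% for the planned one.
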